Name of Sponsor/Company: Alzamend Neuro, Inc.	Individual Study Table Referring to Part of the Dossier	(For National Authority Use Only)
Name of Finished Product: AL001	Volume:	
Name of Active Ingredient: Lithium salicylate/L-proline cocrystal	Page:	
Conclusion: 
Under the conditions of this study, multiple dose administrations of AL001 was well tolerated in healthy elderly and non-elderly subjects, and in subjects with AD, regardless of their comorbidities and concomitant medications.The observed AL001 MTD (1680 mg given TID at 8 AM, 2 PM, and 8 PM, total daily dose 5040 mg) provided lithium at a lithium carbonate equivalent dose of 240 mg TID (720 mg daily) or a lithium citrate oral solution or syrup (8 mEq/5 mL) equivalent dose of 4 mL TID (19.2 mEq daily), all under fasted conditions. The MTD was selected to mitigate or obviate the need for TDM in targeted neurodegenerative, neurological, and neuropsychiatric conditions, at least for subjects without undue renal compromise.With respect to salicylate, these levels of exposure can be justified as safe a posteriori since they are less than the maximum for prescriptive aspirin/salicylate indications and are to be used for a serious medical condition.No clinically obvious or relevant lithium or salicylate PK differences were observed between non-elderly and elderly healthy subjects, under the conditions of this study.No obvious demographic characteristics were observed under the conditions of this study that can be used to improve successful future enrollments when screening subjects.		
Date of Report: 2024/10/30

1 INTRODUCTION

This statistical analysis plan (SAP) provides a detailed description of the statistical methods and procedures to be implemented for the analyses of data from protocol AL001-ALZ02. The analyses described in the SAP are based upon the final protocol version 8.0 (Amendment 06) dated 2022/11/28.

2 STUDY OBJECTIVES

The objectives of the study and corresponding study endpoints are detailed in Table 1.

Table 1: Objectives and Related Endpoints

Objective	Endpoint	Analysis
Primary		
To evaluate the safety and tolerability of AL001 under multiple-dose, steady-state conditions in Alzheimer's subjects and healthy adult subjects.	
 • Vital signs (blood pressure, heart rate, and oral body temperature) • 12-lead electrocardiogram • Physical examination • Safety laboratory tests (hematology, chemistry [including thyroid-stimulating hormone (TSH), vitamin B12, and Mg], HbA1c, and urinalysis • Reported and observed Adverse events (AEs)/serious AEs)/tolerability observations including signs and/or symptoms of lithium and/or salicylate toxicity 	Refer to Section 8
Secondary		
To characterize the Maximum tolerated dose (MTD) of AL001 in patients with mild to moderate Alzheimer's disease (AD) and healthy adult subjects.	
 • Prevalence of peak salicylate concentrations above 30 mg/dL • Prevalence of trough plasma lithium concentrations above 1.2 mEq/L for healthy adult subjects or 1.0 mEq/L for healthy elderly and Alzheimer's subjects. 	Refer to Section 7
Exploratory		
To explore the difference in PK profile between the non-elderly vs elderly subjects (healthy subjects only).	
 • Descriptive statistics for PK will be presented by treatment group and compared between non-elderly and elderly subjects. 	Refer to Section 7
For AD subject cohorts (Cohorts 1, 2b, 3b, 4b, and 5b), determination of qualitative and quantitative evaluations of AD subject desirable characteristics for future Phase 2 and 3 clinical studies in order to: 
 • facilitate recruitment into subsequent AL001 clinical trials • facilitate trial-adherence to completion of study requirements including treatment adherence 	
 • Demographic characteristics of all screened and successfully enrolled AD subjects will be documented to determine what AD subject characteristics are needed and appropriate for successful recruitment and adherence to treatment and study requirements in future Phase 2 and 3 clinical studies. Baseline Mini-Mental State Examination scores, FDA classifications (protocol APPENDIX 3) and demographic characteristics, for example, will be reviewed for relationship to AD subjects' ability to provide informed consent and complete study requirements. 	Refer to Section 6

3 STUDY DESIGN

3.1 General Description

This is a Phase 1/2a, multi-center, double-blind, placebo-controlled, randomized, MAD clinical study to determine the safety and MTD of AL001 in subjects with mild to moderate AD (FDA Classification of Stage 2 to 4 AD [protocol APPENDIX 3]) and healthy adult subjects. Cohorts 1, 2b, 3b, 4b, and 5b will include AD subjects (between the ages of 50 and 80 years, inclusive) and Cohorts 2a, 3a, 4a, and 5a will include healthy subjects (non-elderly adults between the ages of 18 to 64 years, inclusive, and healthy elderly adults between the ages of 65 to 80 years, inclusive). In each of the 9 cohorts, subjects will be confined to the study site from Day -1 until Day 15.

The study consists of 3 phases.

1. Screening Phase – up to 28 days (from Days -28 to -1)
2. Treatment Phase – 16 days:
 - Subjects will be admitted to the study site on Day -1. Subjects will receive 14 days of 3 times daily (TID) dosing with assigned study medication from Days 1 to 14 and will remain confined until Day 15.
 - Each of the 9 cohorts will be initiated sequentially starting with Cohort 1 and progressing through to Cohort 5 depending on acceptable review of the safety data by a 3-member expert adjudication panel. Each of the Cohorts 2 to 5 will be subdivided into 2 cohorts: Cohorts 2a, 3a, 4a, and 5a will include healthy subjects and Cohorts 2b, 3b, 4b, and 5b will include AD subjects. The results from the healthy subject cohorts ‘a’ will be reviewed by the independent safety adjudication committee and if assessed as safe, the committee will permit progression to the corresponding AD subject cohort ‘b’ at the same dose level, as well as progression to the next dose level of healthy subject cohort. The healthy subject cohorts can proceed to the next higher dose level without having to wait for the corresponding AD subject cohort to be completed and reviewed by the safety adjudication panel.
 - The initiation of the next dose cohort may be delayed up to approximately 4 weeks following the last dose of the last subject in the preceding cohort. This is necessary to allow time for the safety and PK data to be compiled and tabulated for review by the safety committee (laboratory reports, AEs, tolerability, and PK data from all [up to 8] completed subjects in each cohort), to determine if it is safe to proceed with enrollment of the subsequent cohort.
3. Follow-up Phase - 1 month
 - Subjects will be followed-up after discharge from the study site on Day 15, with a post-treatment clinic visit on Day 23 and a post-treatment telephone call on Day 42.

Each patient will participate in the study for up to approximately 2.5 months.

3.2 Treatments

Cohort 1 will include 8 AD subjects (6 active and 2 placebo). Each of the Cohorts 2 to 5 will be sub-divided into 2 cohorts: Cohorts 2a, 3a, 4a, and 5a will include healthy subjects and Cohorts 2b, 3b, 4b, and 5b will include AD subjects. For each cohort, subjects will be randomized to 1 of 2 treatment groups in a 6:2 ratio of AL001 (active study medication) to placebo. Subjects in each of the cohorts will be dosed TID for 14 days at the dose level indicated in Table 2 below or placebo

Active Group: Ascending doses of AL001 are manufactured in 210 mg 0 size capsules; the number of capsules for each cohort dosing will vary based on the AL001 dosing equivalent (refer to Table 2). Dosing will be TID at approximately 8:00 AM, 2:00 PM, and 8:00 PM (within ± 10 minutes). Patients will be fasted for each dose (dosed at least 1 hour before or 4 hours after meals).

Placebo Group: The placebo capsules will be manufactured to appear exactly as the capsule used for AL001; the number of capsules dosed, number of doses, dosing schedule, and fasting conditions will be the same as for the active group.

Table 2: Ascending Doses of AL001 for Each Cohort

Cohort	Daily Dosing Level	No. of AL001 210 mg Capsules	AL001 Daily Dose Equivalent
Cohort 1	60% of 450 mg lithium carbonate	3 capsules TID	1890 mg \times 14 days
Cohort 2a/ Cohort 2b	100% of 450 mg lithium carbonate	5 capsules TID	3150 mg \times 14 days
Cohort 3a/ Cohort 3b	140% of 450 mg lithium carbonate	7 capsules TID	4410 mg \times 14 days
Cohort 4a/ Cohort 4b	160% of 450 mg lithium carbonate	8 capsules TID	5040 mg \times 14 days
Cohort 5a/ Cohort 5b	200% of 450 mg lithium carbonate	10 capsules TID	6300 mg \times 14 days ^a

Abbreviation: TID = 3 times daily.

a. Lithium dose equivalent to that used for bipolar/affective disorders.

3.3 Study Procedures

For complete details on the study assessments to be performed, refer to [APPENDIX A](#).

3.4 Randomization and Blinding Procedures

Subjects will be randomized by computer in a ratio of 6:2 (active:placebo) in each of the 9 cohorts. The randomization will be performed separately for AD subject cohorts and healthy subject cohorts. For the AD subject cohorts (Cohorts 1, 2b, 3b, 4b, and 5b) subjects will be randomized in a 6:2 ratio (active:placebo) and for the healthy subject cohorts (Cohorts 2a, 3a, 4a, and 5a), the randomization will be performed in such a way that age will be used as a stratification factor for each cohort: 3 non-elderly and 3 elderly subjects will receive AL001, and 1 non-elderly and 1 elderly subject will receive placebo.

The subjects will be assigned a Screening Number (upon signing the informed consent at the Screening Visit) and a Subject Randomization Number (upon meeting eligibility criteria on Day 1) sequentially by the Investigator or authorized study staff. The Subject Randomization Numbers will start with 1001 for Cohort 1, 2001 for Cohort 2, etc. Prior to dosing on Day 1, the subject is assigned the next sequential randomization number for that cohort. Once a Subject Randomization Number is assigned to a subject, it will not be reused. The subject ID number will be the combination of the Screening Number and the Randomization Number.

A key to the randomization will be kept secured by the Sponsor's Medical Monitor or other Sponsor representative not involved in this study, in a sealed envelope under secure conditions at the study site for emergency use. In the occurrence of an SAE, or other safety issue which requires knowing the patient's treatment group, the Medical Monitor will unblind that patient.

3.5 Sample size

A maximum of 5 cohorts of 8 AD subjects each and 4 cohorts of 8 healthy subjects each will be enrolled in this clinical trial for a maximum total of 72 subjects. Each cohort will correspond to one of the 5 given dose level of AL001 and will be comprised of 6 subjects receiving AL001 and 2 subjects receiving placebo. This sample size is not based on any statistical considerations, but is judged adequate to meet the primary objective of this clinical trial.

4 ANALYSIS POPULATIONS

The following analysis sets will be defined:

- **Screened Analysis Set:** The Screened Analysis Set will include all the subjects who have signed the informed consent form.
- **Randomized Analysis Set:** The Randomized Analysis Set will include all subjects who are randomized within one of the cohorts.
- **Safety Analysis Set:** The Safety Analysis Set will include all subjects in the Randomized Analysis Set who receive any dose of study drug. This analysis set will be utilized for all safety analyses.
- **Pharmacokinetic Analysis Set:** The PK Analysis Set will include all subjects in the Safety Analysis Set who receive AL001 and have either a Cmax measurement for salicylate or a trough measurement for lithium. This analysis set will be utilized for all PK analyses.

5 STUDY SUBJECTS

Disposition data, analysis population information, and protocol deviations will be listed and summarized as described in Table 3.

Table 3: Data Presentations for Study Subject Information

Data	Variables	Presentation
Disposition and analysis population	Subject, completion status (i.e., completed or withdrawn), reason for withdrawal, analysis set determination	Listings: 
• Randomization• Disposition• Analysis set Table: 
• Disposition
Protocol deviations	Protocol deviations	Listings: 
• Protocol deviations

5.1 Disposition

Subject disposition will be summarized for all subjects randomized. The following will be presented:

- Number of subjects (N) screened
- N of subjects randomized
- N and % of subjects who completed the study
- N and % of subjects who withdrew from the study by primary reason for withdrawal
- N and % of subjects included in each analysis set

The percentages will be calculated using the number of randomized subjects as the denominator. The summary will be presented by treatment (dose level of AL001, pooled placebo and overall) for AD cohorts and Healthy cohorts.

5.2 Protocol Deviations

Deviations identified at the site will be collected in the clinic deviation tracking system (DTS) and presented in a protocol deviation listing. Protocol deviations will be reviewed by the Sponsor, principal investigator, and lead statistician and finalized before unblinding the study. Protocol deviations will be listed for the safety population.

6 DEMOGRAPHIC AND OTHER BASELINE CHARACTERISTICS

Unless otherwise specified, all available data will be listed, summarized, for demographics and other baseline characteristics, and presented for all study population as detailed in Table 4. The screened analysis set will be used for exploratory analysis.

Table 4: Data Presentations for Demographic and Other Baseline Characteristics

Data	Variables	Presentation
Demographic and Other Baseline Characteristics	Sex, age, ethnicity, race, height, weight and body mass index (BMI), Mini-Mental State Examination (MMSE) scores, and AD stage FDA classification for AD subjects only	Listing Table – presented for all study populations (Screened, Randomized, Safety and PK).
Medical history	All medical history findings	Listing
Prior and Concomitant medications	All medications taken prior to study drug administration and concomitant medications	Listing

7 PHARMACOKINETIC ANALYSES

7.1 Pharmacokinetic Statistical Methodology

All PK tables, figures and listings (TFLs), when appropriate, will be stratified by treatment and cohort for each study part.

7.2 Summary Statistics

In order to characterize the MTD of AL001 in subjects with AD and healthy subjects, descriptive statistics will be presented by treatment group for each cohort and overall for the following:

- Proportion of healthy non-elderly subjects with trough lithium concentrations $> 1.2 \text{ mEq/L}$
- Proportion of subjects with peak (Cmax) salicylate concentrations $> 30 \text{ mg/dL}$
- Proportion of healthy elderly and, separately, Alzheimer's subjects with plasma trough measurements of lithium $> 1.0 \text{ mEq/L}$

Summary statistics of the plasma concentration data will be calculated for the PK population, unless otherwise indicated. Summary statistics will be calculated for concentration at each individual time point.

Concentration data will be summarized by treatment group and compared between non-elderly and elderly subjects only for healthy cohorts using the following statistics: number of observations (N), arithmetic mean (mean), standard deviation (SD), geometric mean, minimum (min), median, maximum (max), and coefficient of variation (CV%).

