7.3 Statistical Analysis

In order to assess whether PK steady state has been approximately achieved, descriptive statistics for trough (Cmin) measurements of plasma lithium and Cmax (peak) measurements of plasma salicylate will be presented for all available days by cohort and overall. In addition, these measurements for plasma lithium and salicylate on Days 13 and 14 for each cohort will be \log^e -transformed and a 90% CI for the difference in the measurements between Days 13 and 14 for lithium and salicylate will be calculated on the \log^e scale and then transformed back to the original scale for each cohort. If the 90% CI on the original scale is contained within the interval 85.0% to 117.6%, then an approximation of steady state will be concluded for the respective analyte and cohort. Alternative approaches to estimate achievement of steady-state conditions are to be used, as appropriate, such as when at least 3 trough concentrations for plasma lithium and/or at least 3 Cmax concentrations for plasma salicylate can be assessed using linear regression. All cohorts except Cohort 1 are expected to complete at least 3 lithium trough and 3 salicylate peak concentration measurements and should be candidates for this statistical approach.

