8 SAFETY ANALYSIS

Unless otherwise specified, all available data will be listed and summary tables for safety assessments will be presented by treatment (dose level of AL001 and pooled placebo) per cohort for the safety population as detailed in Table 5 and all applicable safety data will be presented by combined active and pooled placebo groups, such as, disposition, demographic, adverse events, labs, vital signs, and 12-ECG data.

Continuous variables will be summarized (absolute values and change from baseline) using descriptive statistics (n, mean, SD, minimum, median and maximum).

Table 5: Data Presentations for Safety Assessments

Data	Variables	Presentation
Adverse events	Adverse event (AE) description, date and time (start and end), intensity, relationship to study drug, action taken, study days and outcome	Listing Table
Extent of exposure	Study drug administration dose, units, date, time, cohort	Listing
Clinical laboratory evaluations	Laboratory results (refer to section 8.3 for parameters)	Listing Table
Vital signs	Blood pressure, pulse, and body temperature	Listing Table
Physical examinations	Physical examinations findings	Listing
12-Lead ECGs	ECG interpretations and findings	Listing Table

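### Optional: for the exploratory elderly v non-elderly PK question, add a pooled, dose-adjusted ratio with 90% CI to the planned 3 v 3 descriptive tables

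*SAP*

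**What the plan says.** The age comparison is an exploratory objective. Its endpoint in SAP Section 2, Table 1 reads: "Descriptive statistics for PK will be presented by treatment group and compared between non-elderly and elderly subjects". Section 7.2 carries this out. Concentrations are summarised by treatment group and "compared between non-elderly and elderly subjects only for healthy cohorts using the following statistics", followed by N, arithmetic mean, SD, geometric mean, minimum, median, maximum and CV%. The list contains no ratio, model or interval for age.

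Three further passages fix the size of the comparison:

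- **Allocation.** SAP 3.4 states that "age will be used as a stratification factor for each cohort: 3 non-elderly and 3 elderly subjects will receive AL001".
- **Layout.** SAP 7.1 says that PK outputs, "when appropriate, will be stratified by treatment and cohort for each study part". SAP 8 explains treatment as dose level for the safety tables, which "will be presented by treatment (dose level of AL001 and pooled placebo) per cohort".
- **Sample size.** SAP 3.5 says: "This sample size is not based on any statistical considerations".

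The only confidence interval in Section 7 of the SAP concerns steady state: "a 90% CI for the difference in the measurements between Days 13 and 14 for lithium and salicylate will be calculated", on the log scale and by cohort.

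The protocol synopsis reports 24 healthy subjects in the PK Analysis Set and describes descriptive methods for the age question. It concludes that, under the study's conditions, no clinically obvious or relevant lithium or salicylate difference between the age groups was observed.

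**The concern.** Read by dose level, the plan sets 3 elderly beside 3 non-elderly subjects, four times over, for each analyte and day. It never combines the four comparisons. Randomisation was stratified by age within each healthy cohort, so the design supports one pooled, dose-adjusted contrast that the planned outputs do not report.

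At stake is how the synopsis conclusion can be read. A statement that no relevant difference was observed may rest on data that exclude all but small differences, or on data that leave large ones open. Without an estimate and its precision, the reader cannot tell which. Age also matters elsewhere in the plan, since the secondary endpoint uses different lithium thresholds for elderly and non-elderly healthy subjects.

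**Working it through.** **The plan's own counts.** The planned maximum is 5 x 8 + 4 x 8 = 72 (SAP 3.5). Healthy subjects on AL001 number 4 cohorts x (3 + 3) = 24, which matches the 24 in the synopsis. If the planned split was achieved, that is 12 v 12 overall and 3 v 3 per dose. The documents state no precision for the age comparison, so there is no figure of that kind to reproduce.

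**Assumption.** The documents give no between-subject CV for trough lithium or peak salicylate. I take 20%, 30% and 40%. The log-scale SD is s = sqrt(ln(1 + CV^2)) = 0.198, 0.294 and 0.385.

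**Formula.** The 90% CI around an observed ratio of 1 is exp(-/+ h x s), where h = t(0.95, df) x sqrt(1/n1 + 1/n2).

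- Dose-adjusted model, 12 v 12: df = 24 - 5 = 19 (four dose terms and one age term), so h = 1.729 x sqrt(2/12) = 0.706.
- One cohort, 3 v 3: df = 4, so h = 2.132 x sqrt(2/3) = 1.741. The SAP does not plan this interval; it is shown for scale only.

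| Assumed CV | 12 v 12, dose-adjusted | One cohort, 3 v 3 |
|---|---|---|
| 20% | 0.87-1.15 | 0.71-1.41 |
| 30% | 0.81-1.23 | 0.60-1.67 |
| 40% | 0.76-1.31 | 0.51-1.96 |

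**Missing values.** The synopsis reports 2 discontinued healthy subjects and does not give their arm. Suppose both were on AL001 and had no Day 13-14 value. Then 22 subjects remain and df = 17. Enumerating every placement over the 8 dose-by-age cells gives three values of h:

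- 0.742 when one is lost from each age group at the same dose;
- 0.749 when they are lost from different doses;
- 0.759 when both are lost from one cell.

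At CV 30% the interval is then 0.80-1.24 to 0.80-1.25.

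**What the planned tables already hold.** In a cell of 3, the minimum, median and maximum are the three observations. In a cell of 2, the minimum and maximum are both of them. By-dose, by-age tables for a given day therefore contain every value for that day, and the model could be refitted from them. With complete balanced data, the geometric mean of the four by-dose ratios also equals the model's ratio.

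**Which days to use.** SAP Appendix A schedules post-baseline samples on Days 3, 5, 7, 10, 13 and 14. Averaging over all of them assumes one age ratio throughout accumulation. As an illustration, assume a one-compartment model, the planned dose times, instantaneous absorption, and half-lives of 24 h (non-elderly) and 36 h (elderly). The trough ratio is then 1.29 on Day 3 and 1.59 on Days 13 and 14, and the six-day average is 1.50. The early days pull a real steady-state difference towards 1, so Days 13-14 should be primary.

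**The case against.** The strongest reply is that nothing is wrong. The objective is exploratory, the endpoint is descriptive by definition, the sample size is openly non-statistical, and no planned decision turns on an age ratio, because the MTD is characterised by threshold proportions. The synopsis conclusion is also limited to what was observed under the study's conditions. All of this stands, and it is why the point is optional. It does not remove the case for an interval, which is estimation and needs no alpha, power or margin.

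A second reply also stands. A reader might infer that the plan throws away the information needed for an interval. The documents do not support that: the small-cell summaries reveal the individual values, and SAP 7.1 provides for PK listings. The interval is unplanned, not lost.

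A reader might also infer that the synopsis claims equivalence on inadequate data. It does not. It excludes no particular ratio, and the documents set no age margin. The full report tables are not among the documents, so the point concerns the plan only.

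Finally, SAP 3.2 uses treatment groups to mean AL001 v placebo. If Section 7.2 meant that, the age summaries would mix daily doses from 3150 to 6300 mg, and individual values would have to come from the listings. A ratio and interval would still be absent.

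**Conclusion.** This is an optional, inexpensive improvement, not an error or a contradiction. The SAP plans side-by-side descriptive statistics for age, with 3 v 3 on AL001 per healthy dose level and no pooled estimate, while the synopsis draws a conclusion on the question. The planned sample could support a 90% CI of 0.87-1.15 to 0.76-1.31 around a ratio of 1, for assumed CVs of 20% to 40%. At CV 30% it is 0.81-1.23, or at most about 0.80-1.25 if two AL001 subjects lack values.

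These figures assume the planned 12 v 12 split, one value per subject, and a common age ratio and log SD across doses. The interval would describe precision and would not by itself show similarity. At a CV of 40% it still allows differences of about 30%.

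**What to change.** Keep the planned tables. For lithium trough and salicylate peak separately, add a log-scale model in healthy AL001 subjects, with dose level and age stratum as factors. Use each subject's Day 13-14 mean of the log values as the primary measure, and state how a subject with only one of the two days is handled. Dose as a factor avoids assuming dose proportionality. Report the elderly/non-elderly geometric mean ratio, its 90% CI and the number of subjects per age group. Word the age statement from the interval, for example by naming the ratios it excludes.

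A repeated-measures analysis over Days 3-14 can be secondary. It needs a subject effect and an age-by-day term, with the ratio read at Days 13-14.

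The cost is one model per analyte on existing data and a sentence in the report. The downsides are these:

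- Cells of 3 v 3 can hardly check the common-ratio and common-SD assumptions.
- Age was a stratum, not a randomised factor, so the contrast is observational, and differences in weight, sex or renal function remain in it.
- The PK Analysis Set takes subjects "who receive AL001 and have either a Cmax measurement for salicylate or a trough measurement for lithium", so fewer than 24 may be usable for one analyte.
- The ratio describes trough and 1.25-hour samples, not a full profile.
- The study is complete, so the analysis must be labelled post hoc.
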